The Impact of Frailty on the Postoperative Outcomes of Gastric Cancer Surgery (TOREGA)

05/16/2018

SUMMARY

Background. Gastric cancer is an important health care problem even though treatment advances, and it is diagnosed mainly in elderly. Surgery is the main treatment for gastric cancer and is associated with a high rate of postoperative complications and mortality, even higher in older patients. Chronological age seems not to be the main factor influencing the worse outcome of older patients, comorbidities and frailty have also been taken into account recently.

Methods. Participation in the study will be offered to all centers that are currently part of the Spanish EURECCA (EUropean REgistry of Cancer CAre) Esophagogastric Cancer Registry. The impact of the frailty on different outcome variables will be evaluated. The main outcome variable will be 90-day mortality after the intervention. Health-related quality of life (HRQoL) will also be evaluated.

Objective. The objective of the study is to value the impact of frailty on gastric cancer surgery outcomes therein the Spanish EURECCA Esophagogastric Cancer Registry.

Introduction

Gastric cancer is the fifth most frequent cancer and the third cause of death due to cancer. The increase in life expectancy cause it to be diagnosed more and more in elderly people, with an average age at diagnosis of 68 years in the West (1, 2).

Surgery is the main treatment for gastric cancer and is associated with a high rate of postoperative complications and mortality, which is even higher in elderly patients (data from the ACS-NSQIP between 2007 and 2013: 30-day severe morbidity from 16.3% in 80 years and 30-day mortality from 1.2% in 80 years) (3).

Generally, advanced chronological age is considered a negative prognostic factor for complications and hospital stay in major surgery (4). Age per se, however, seems to be responsible only in part for the increased risk of postoperative complications (5).

Greater risks seem to be associated with other factors such as comorbidities, so, in the preoperative evaluation, variables such as the Charlson comorbidity index have been introduced (6, 7). Another variable that has emerged recently for the estimation of perioperative risk is frailty (8), which is defined as "a medical syndrome with multiple causes and contributors that is characterized by a decrease in strength, endurance and physiological capacity, which increases the risk of the vulnerability of the individual and/or death" (9). Surgery is a major stress factor that can disrupt physiological homeostasis; therefore, frailty has a clinical significance when considering surgery in elderly patients (6).

There are two main ways to measure frailty: one by clinical definitions of a fragile phenotype (10) and another by frailty indexes that assess the accumulated deficits in multiple domains (11). Measures to assess frailty are numerous and this is a limitation when standardizing and comparing studies (12); among the most used there are the Fried criteria (10), the frailty index of the Canadian Study of Health and Aging (CSHA-FI) (13) and the modified frailty index of Velanovich (mFI: modified Frailty Index) (14).

Other indices widely used in the clinic are the Geriatric 8 (G8) (15), which is recommended above all in elderly patients with cancer (16) and the Groningen index (GFI: Groningen Frailty Indicator) (17). The prevalence of frailty in elderly patients (65 years or older) is highly variable, probably due to the diversity in the definitions of frailty (4.0-59.1% in community residences, 10.4-56.0% in patients who are candidates for elective surgery) (18, 19, 20). The prevalence of frailty increases in females and with age (being 15.7% in patients aged 80-84 years and 26.1% in patients older than 85 years) (18).

Frailty appears in several studies as a more important indicator than chronological age with respect to postoperative results (20, 21, 22, 23). There are evidences that relate frailty, evaluated with different indices, with the increase of postoperative complications, hospital stay, need of discharge to convalescence centers, health costs, short and long term mortality, after major surgery (12, 20, 22, 24, 25, 26, 27, 28, 29).

Therefore, it is important to identify fragile patients to implement prevention programs through global geriatric assessments (CGA Comprehensive Geriatric Assessment). Just by having more clinical attention for more fragile patients after major surgery there can be better results of short and long-term postoperative mortality (22). Likewise, as demonstrated in randomized clinical studies, prehabilitation and global geriatric assessment programs improve the results in terms of postoperative complications and hospital stay (30, 31, 32).

The CGA is an established method to evaluate and optimize the physical state, the psychological, functional and social problems in elderly patients in order to improve the results of the treatments. It implies an interdisciplinary evaluation of multiple domains, followed by planning for analysis, treatment, rehabilitation and long-term follow-up (33).

This allows, in the first place, to intervene before an operation, to increase the physiological reserve of a patient, especially with exercise and nutrition (34, 35). In addition, the therapeutic decision can be guided by adapting the surgical recommendations to the physiological capacity of the patient; second, the knowledge of the increased risk of complications and the possible need for transfer to institutions (especially in patients who live alone) prepares patients and their families for postoperative evolution (8).

The majority of studies published in the literature on the relationship between frailty and postoperative results are retrospective studies, which evaluate populations of patients undergoing major surgery and who, in general, analyze short-term results (30-day mortality) (12, 20, 22, 24, 25, 26, 27, 28, 29). None of these takes into account the impact of surgery on the quality of life of this group of patients. Among all these studies there is very little information about the influence of frailty in gastric cancer surgery. There is only one retrospective study that focuses only on gastric cancer surgery, using the Groningen index and revealing an increase in in-hospital mortality and serious complications (Clavien-Dindo complications score ≥ 3) in fragile patients (25). Objective

The aim of the present study is to assess the impact of frailty on the results of gastric cancer surgery (long-term postoperative morbidity and mortality, hospital stay, readmissions, need of transfer to institution of medium or long stay and quality of life).

Methods

Study design: Patients and participating Centers This is a prospective and multicenter cohort study, within the Spanish EURECCA Esophagogastric Cancer Project, to investigate the impact of frailty on the postoperative results of surgery for gastric cancer in elderly patients. Inclusion/exclusion criteria will be following:

- Inclusion criteria: Patients ≥ 70 years diagnosed with gastric cancer (whether or not they have received neoadjuvant treatment) and candidates for elective surgical resection with potentially curative intention (R0) even if it is finally an R1 or R2.
- Exclusion criteria: Patients with disseminated gastric cancer or candidates for palliative surgery, as well as those patients who do not give their consent to participate. Participation in the study will be offered to all centers that are currently part of the Spanish EURECCA Esophagogastric Cancer Registry. Those hospitals that show their desire to participate must sign the Letter of Commitment.

The Spanish EURECCA Upper GI Cancer Group was created in 2012 and collects prospective and validated information about all the patients submitted to surgery for esophagogastric cancer in the public hospitals of four Spanish Autonomous Communities, with the aim of having reliable information on the results of this surgery and constitute a platform for the development of research projects.

Data collection

A specific on-line database will be created for this project, with all the security measures (user and password for individual access), in which the researchers will record the data referring to the Frailty and Quality of life questionnaires. On this basis, the researcher will use the patient identifier (random 6-digit code) previously established by the on-line registration of the EURECCA Project where the patients variables are usually collected.

Primary and secondary variables The impact of the frailty on different outcome variables will be evaluated. The main outcome variable will be 90-day mortality after the intervention. Other secondary outcome variables will also be evaluated: incidence of serious complications (Clavien-Dindo complications score ≥ 3), Complication Comprehensive Index (CCI) score (37, 38), hospital stay, incidence of death in patients suffering from a complication (failure to-rescue), hospital readmission within the first 30 days after the discharge, destination of the patient after discharge from hospital [home, social health centers, or geriatric residence], mortality at 12 months after the intervention, quality of life before the intervention and at 12 months.

Frailty evaluation For the assessment of frailty (frailty screening), two questionnaires will be used:

- Questionnaire G8: This is a questionnaire with 8 questions, easy to use, with a total score that varies from 0 to 17 points. Previous studies suggest the score ≤ 14 as a cut-off point to identify the fragile patient, with a sensitivity of 92% and specificity of 52% (36).
- Modified frailty index: This index was described by Velanovich et al. (14), based on a previously validated simplification of the frailty index CSHAFI (Canadian Study of Health and Aging Frailty Index), which was specifically designed to analyze data included in the National Surgical Quality Improvement Program of the American College of Surgeons (ACSNSQIP). It consists of 11 questions with 1 point assigned to each of them on the functional, endocrine, respiratory, cardiovascular and neurological status of the patient. It allows to divide the patients into 4 groups: without frailty (FI = 0), slightly fragile (FI = 1), moderately fragile (FI = 2) and severely fragile (FI ≥ 3).

Postoperative complications Postoperative complications will be classified according to the recommendations proposed by the European Chapter of the International Gastric Cancer Association (EGCA) (unpublished data), its severity through the classification of Clavien-Dindo and the CCI (37, 38). In particular, the CCI will be calculated using the free application that can be found on the website: www.assessurgery.com/calculator_single/.

[Health-related quality of life](#)

Health-Related Quality of Life (HRQoL) will be evaluated with the validated Quality of Life questionnaires of the European Organization for Research and Treatment of Cancer (EORTC-QLQ), QLQ-C30 (30 items Core Quality of Life Questionnaire, version 3.0) and with the specific module for gastric cancer QLQ-STO22 (22 items Stomach Quality of Life Questionnaire).

- The EORTC-QLQ-C30 is a questionnaire that reflects the multidimensionality of HRQoL in patients with cancer. It is composed of 30 questions distributed in five functional scales (physical, role, cognitive, emotional and social), three scales of symptoms (fatigue, pain and nausea and vomiting), a global health scale and a series of additional questions to evaluate symptoms commonly referred by patients diagnosed with cancer (dyspnea, loss of appetite, insomnia, constipation and diarrhea) and the perceived financial impact.
- The EORTC-QLQ-STO22 questionnaire contains 22 structured items in five domains (dysphagia, food restrictions, pain, reflux and anxiety) and four specific items (dry mouth, alteration of taste perception, body image and hair loss) related to the symptoms of the disease.

Sample size

The calculation of the sample size is based on the primary objective of comparing fragile versus nonfragile patients with respect to postoperative mortality at 90 days after the intervention. Based on mortality data previously published in a retrospective study by Mosquera et al. (24), it is estimated that mortality for the group of non-frail patients is 0.6% and for the group with frailty 4.3%. From the data of the literature, a prevalence of 23% of frailty is calculated in the population of patients with gastric cancer and age \geq 70 years undergoing gastrectomy (24). For a power of 80% and a level of significance of 95% in a unilateral analysis, it is estimated that 276 non-fragile patients and 92 fragile patients would be needed to detect as statistically significant the difference between the proportion of patients who die between both groups.

Statistical analysis plan

The characteristics of fragile and non-fragile patient groups will be compared through frequency tables. The Chi-square test will be used to compare the differences between the categorical variables and the ANOVA test for the continuous variables. Different analyzes are proposed according to the study variables that are to be analyzed. For dichotomous type response variables (90- day mortality, 12-month mortality, incidence of serious complications, incidence of in-hospital death in patients with complications, and hospital readmission at 30 days after discharge), a multivariate logistic regression will be used to evaluate the risk (odds ratio) of these variables. For continuous response variables (ICC score) at 30 days after the intervention, and number of days of hospital stay), linear regression models will be used. For the variable categorical response of the patient after hospital discharge, an ordinal logistic regression model will be done. All regression models will be adjusted for age, sex, body mass index (BMI), type of gastrectomy, center volume, neoadjuvant treatment and degree of frailty. Regarding HRQoL analysis, the mean scores and 95% confidence intervals for the different domains of preoperative HRQoL and one year after surgery will be calculated. Changes of more than 10 points on a scale from 0 to 100 will be considered clinically relevant as previously suggested in other publications (40). Work plan The study period includes: Patient recruitment. Follow-up for 1 year to meet the objectives of the study.

The study starts by assessing the fragility of the patients. Once the stage study is completed, the potential curative surgery is determined and after the case presentation in the Multidisciplinary Tumor Committee of each institution, the G8 questionnaires and modified fragility index will be carried out to identify the state and degree of fragility, 2 weeks prior to surgery. The result of the evaluation of the frailty of the patient, will be performed after the Multidisciplinary Committee, thus it will not modify the therapeutic decision.

To measure the Health Related Quality of Life (HRQoL), the QLQ-C30 and QLQ-STO22 questionnaires, will be delivered at the time of the preoperative visit and 12 months after surgery.

Patients will be asked to fill them in their home. If any patient reports difficulty in understanding the questionnaires, additional help will be provided. Once the questionnaires are received, it will be verified that all the questions have been answered. Otherwise, patients will be contacted in order to complete the questionnaire via telephone. If it is not possible to complete the answers of more than half of the questions on a scale, they will be excluded from the statistical analysis, according to the recommendations of the EORTC (39). All responses from the EORTC QLQ-C30 and STO22 questionnaires will be transformed linearly into scores ranging from 0 to 100 to standardize the score. In functional scales, high scores represent better quality of life (better function) while high scores in symptom scales and items involve more symptoms.

In addition, the variables described in the methodology section will be collected and analyzed:

- Incidence of serious complications (Clavien-Dindo complications score ≥ 3)
- Complication Comprehensive Index (CCI) score during the hospital stay and at 30 days after the intervention
- Incidence of in-hospital death in patients suffering from a complication (failure-to-rescue)
- Hospital stay
- Destination of the patient after hospital discharge
- Hospital readmission within the first 30 days after the discharge
- Mortality at 90 days after the intervention
- Mortality at 12 months after the intervention

In addition to the previously described questionnaires and the main and secondary variables, data related to the prevalence of comorbidities of the patients (Charlson Comorbidity Index, ASA), the stage

study, preoperative optimization, surgical intervention, histopathology and follow-up will be collected. All these data are already systematically collected in the EURECCA Register. Ethical considerations This project is included in the EURECCA Registry, which was presented and approved by the Parc de Salut MAR Clinical Research Ethical Committee (CEIC PSMar) in 2013 in its initial version (nº 2013/5047/I). The amendment of the version, dated 9th June 2016, was approved by the CEIC PSMar and by the respective Clinical Research Ethical Committees of the participating centers. The EURECCA Registry also has a specific Patient Information Sheet and Informed Consent, approved in the 1.2 version of March 2018.

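### Discharge destination is analysed without residence before surgery, so a return to an institution can be counted as a new transfer and can bias the frailty odds ratio for this secondary outcome

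*Combined protocol and SAP*

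**What the plan says.** The Objective section lists among the results to be assessed the "need of transfer to institution of medium or long stay and quality of life". Primary and secondary variables turns the first of these into "destination of the patient after discharge from hospital [home, social health centers, or geriatric residence", and the Work plan restates it simply as "Destination of the patient after hospital discharge". Neither place mentions where the patient lived before admission.

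The Statistical analysis plan states: "For the variable categorical response of the patient after hospital discharge, an ordinal logistic regression model will be done". It then closes the covariate list: "All regression models will be adjusted for age, sex, body mass index (BMI), type of gastrectomy, center volume, neoadjuvant treatment and degree of frailty".

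The exclusion criteria are "Patients with disseminated gastric cancer or candidates for palliative surgery, as well as those patients who do not give their consent to participate", so people living in an institution can be enrolled. The Work plan names further items, beginning with "data related to the prevalence of comorbidities of the patients (Charlson Comorbidity Index, ASA), the stage" and going on to preoperative optimization, surgery, histopathology and follow-up. It says that the registry already collects them. Prior residence is not named. On the project's own data, the Data collection section says "A specific on-line database will be created for this project", to hold the frailty and quality-of-life questionnaires. Other patient variables come from the registry, whose full variable list is not in the document.

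**The concern.** Needing a transfer to an institution is most naturally read as an event that follows surgery. A patient who already lives in a geriatric residence is not at risk of that event in the same sense as a patient who lives at home, yet the recorded variable can place both in the same category.

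This matters for the frailty comparison because prior residence may be related to frailty. The modified frailty index includes functional status, and dependent patients are plausibly both frailer by that index and more often in residential care. The Introduction itself links the possible need for institutional transfer to living alone, so the protocol recognises that the home situation bears on this outcome. The analysis does not take it up.

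At stake is the reading of one outcome named in the aim. An association between frailty and institutional discharge could partly reflect where frail patients lived beforehand. The Introduction envisages using knowledge of this risk to prepare patients and families, so an inflated estimate would carry into that advice.

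**Working it through.** **Figures in the plan.** The document gives no rate, effect size or power for discharge destination, so there is no figure to reproduce. The planned group sizes, 276 non-frail and 92 frail (Sample size section), are used only for scale.

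**Assumptions (not in the documents).** Let *q* be the rate of new institutional discharge among patients living at home, equal in both groups, so that the true odds ratio is 1.00. Let *r* be the share already in an institution, all of whom return there and are recorded as such. The three destinations are collapsed to institution versus home, without adjustment.

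**Formulas.** Observed institutional proportion P = r + (1 − r)q. Odds ratio = [P_frail/(1 − P_frail)] / [P_non-frail/(1 − P_non-frail)].

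**With q = 8%:**
- Non-frail, r = 1%: P = 0.01 + 0.99 × 0.08 = 0.0892.
- Frail, r = 3%: P = 0.03 + 0.97 × 0.08 = 0.1076; odds ratio (0.1076/0.8924)/(0.0892/0.9108) = 1.23.
- Frail, r = 5%: P = 0.05 + 0.95 × 0.08 = 0.1260; odds ratio 1.47.
- Frail, r = 8%: P = 0.08 + 0.92 × 0.08 = 0.1536; odds ratio 1.85.

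In patients, 3% to 8% of 92 is 2.8 to 7.4 prior residents in the frail group, and 1% of 276 is 2.8 in the non-frail group.

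**Sensitivity to the assumptions.** With r of 1% v 3% and q = 20%, the odds ratio falls to 1.10. With 1% v 10% and q = 5%, it rises to 2.68. With equal prior residence (3% v 3%), it is 1.00 whatever the value of q.

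**Set against sampling error.** Expected counts at 276 and 92 patients give crude Wald 95% intervals:
- 1.23 (0.57 to 2.68), z = 0.5
- 1.47 (0.70 to 3.09), z = 1.0
- 1.85 (0.92 to 3.74), z = 1.7

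The bias is systematic, but in the two milder cases it is small beside the noise. In the third, z is only just above the one-sided 5% value of 1.645, so a false positive at that level would occur about half the time.

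**If returning residents were coded as home.** Then P = (1 − r)q. For 5% v 1% this is 0.95 × 0.08 = 0.0760 against 0.99 × 0.08 = 0.0792, an odds ratio of 0.96. The result therefore depends on a coding rule that the plan does not state.

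**The case against.** The strongest reply is that transfer may simply mean movement from the hospital to an institution. The Introduction describes the related outcome in the literature as discharge to convalescence centers. On that reading, destination measures the aim directly, and the difficulty mainly concerns geriatric residence, not medium-stay care. This narrows the point but does not remove it: for a returning resident, the destination still says nothing about a need created by surgery.

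A reader might also infer that the plan scores a geriatric residence as a bad outcome. The document does not say so. It lists three destinations, states no order and gives no rule for returning residents. A ranking is implied only by the choice of an ordinal model.

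A reader might further infer that the plan must produce a spurious association. That is not supported either. Upward bias requires prior residence to be more common in frail patients, and no rate is given. Among patients selected for elective resection with curative intent, prior residents may be few. The illustration is also crude and binary, whereas the planned model has three categories and adjusts for age, sex and other factors. Adjustment for age may take up some of the difference.

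Finally, the registry may already record prior residence. If it does, no new field is needed, but the outcome definition and the closed covariate list would still leave the information unused.

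**Conclusion.** The gap is real and conditional. As written, the analysis of discharge destination cannot separate a return to an institution from a new admission to one. The frailty odds ratio is biased upward if frail patients more often lived in an institution beforehand and returning residents are recorded under that institution. Under a true odds ratio of 1 and equal prior residence there is no bias.

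The odds ratios of 1.23 to 1.85 show what modest differences could do. They rest on assumed rates and are not predictions for the adjusted ordinal model. It would go too far to conclude that the plan will answer its objective wrongly. The point concerns one secondary outcome and is worth correcting because the change alters what is estimated and costs little.

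**What to change.** Check whether the registry holds residence before admission. If it does, use it; if not, add one field to the project database. Then state in the Statistical analysis plan that:
- the outcome is new institutional discharge;
- the ordinal model is fitted in patients who lived at home before surgery, with the order of the destination categories given;
- patients already living in an institution are reported separately, by frailty group.

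In the illustration above, this restriction returns an odds ratio of 1.00 by construction, because every remaining patient has r = 0.

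The cost is at most one data field, a short addition to the analysis text, and a few patients leaving one secondary analysis. If prior residents prove rare, almost nothing is lost. The primary outcome and its sample size do not change.

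### The planned models contain no comorbidity measure, so they cannot show how much of a frailty association is due to comorbidity, although the Charlson index is collected

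*Combined protocol and SAP*

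**What the plan says.** The Introduction separates two explanations of poor outcome beyond age. On the first it says: "Greater risks seem to be associated with other factors such as comorbidities". It adds that, for preoperative evaluation, "variables such as the Charlson comorbidity index have been introduced". It then turns to the second: "Another variable that has emerged recently for the estimation of perioperative risk is frailty". The Objective concerns the impact of frailty.

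Frailty evaluation names two instruments. Of the modified frailty index it says "It consists of 11 questions with 1 point assigned to each of them", and that these questions are "on the functional, endocrine, respiratory, cardiovascular and neurological status of the patient". Of the G8 it says "This is a questionnaire with 8 questions, easy to use, with a total score that varies from 0 to 17 points", with 14 or below as the suggested cut-off. It lists the items of neither instrument.

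The end of the Work plan says that the study will collect "data related to the prevalence of comorbidities of the patients (Charlson Comorbidity Index, ASA" among other data that the registry already records.

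The Statistical analysis plan gives a single adjustment rule: "All regression models will be adjusted for age, sex, body mass index (BMI), type of gastrectomy, center volume, neoadjuvant treatment and degree of frailty". It does not say which instrument defines the degree of frailty.

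**The concern.** This is an observational comparison of frail with non-frail patients. The plan names a competing explanation, records a measure of it, adjusts for six other factors and leaves this one out. No stratified, sensitivity or added-value analysis uses Charlson or ASA. The descriptive comparison of the two groups might show an imbalance in comorbidity, but not how much of the frailty estimate the imbalance explains.

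The Introduction argues for identifying frail patients so that prevention programmes can follow. A reader of the secondary results (serious complications, complication index, hospital stay) will want to know whether the frailty screen says anything that the recorded comorbidity does not. The planned output will not answer that.

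**Working it through.** **1. Comparing the sections.** The Introduction has comorbidity and frailty as two risk variables. The Work plan has Charlson and ASA collected. The covariate list has age, sex, BMI, surgery type, volume of the centre, neoadjuvant therapy and frailty, but no comorbidity term. Since one rule covers all models, no other model supplies it.

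**2. Overlap by instrument.** Four of the five domains named for the modified frailty index are organ systems and one is functional. Overlap with Charlson is therefore plausible, but the split of the 11 points is not stated and the degree of overlap cannot be computed. For the G8 the text gives no item content, so any association with comorbidity is an open question.

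**3. Size of confounding.** The plan gives no figure to reproduce here. Let p1 and p0 be the proportions with high comorbidity among frail and non-frail patients, and RR its effect on the risk of serious complications. With no true frailty effect, the apparent frailty risk ratio is

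[1 + p1(RR − 1)] / [1 + p0(RR − 1)].

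All inputs in this table are assumptions.

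| p1 | p0 | RR | Apparent risk ratio |
|---|---|---|---|
| 40% | 30% | 2 | 1.4/1.3 = 1.08 |
| 50% | 25% | 2 | 1.5/1.25 = 1.20 |
| 50% | 25% | 3 | 2.0/1.5 = 1.33 |
| 60% | 20% | 3 | 2.2/1.4 = 1.57 |

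This range is not a bound: 80% v 30% with RR 5 gives 4.2/2.2 = 1.91.

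**4. How often this would look like a finding.** Take the planned 276 and 92 patients, an assumed non-frail risk of 10% to 25%, and the middle factors 1.20 and 1.33. The chance of a one-sided p below 0.05 in an unadjusted comparison is Φ[(d − 1.645·s0)/s1], where d is the risk difference and s0 and s1 are its pooled and unpooled standard errors.
- 10% v 12%: d = 0.020, s0 = 0.0369, s1 = 0.0384, giving 14%.
- 25% v 33.3%: d = 0.0833, s0 = 0.0535, s1 = 0.0556, giving 47%.

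The nominal figure is 5%.

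**5. Which models can carry another term.** From the Sample size section, expected deaths at 90 days are 276 × 0.006 + 92 × 0.043 = 1.66 + 3.96 = 5.6. The listed terms need at least 7 parameters, so there are 5.6/7 = 0.80 deaths per parameter now, and 5.6/8 = 0.70 with Charlson added. That model has no room. For serious complications the plan assumes no rate. The Introduction's 16.3%, from a sentence that is hard to read and so only illustrative, would give 0.163 × 368 = 60 events, or 60/8 = 7.5 per parameter. Complication index and stay are continuous and draw on all patients.

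**6. Price in precision.** Let R² be the share of variation in G8 status that Charlson explains beyond the other covariates. Interval width then grows by about √[1/(1 − R²)]: 1.05 for an assumed R² of 0.10, 1.15 for 0.25 and 1.41 for 0.50.

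**The case against.** The strongest reply is that the omission may be the right choice. The Introduction defines frailty as a syndrome of many causes and describes frailty indexes as adding up deficits across domains. On that view comorbidity is partly a component or cause of frailty, and adjusting for it would remove some of the exposure. The comparator that the Introduction stresses is chronological age, which is in the model. Frailty beyond Charlson is not a stated objective.

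Much of this stands. It is a good reason not to put Charlson into the modified frailty index model, and a good reason to keep the unadjusted estimate. It does not remove the gap, because the plan never says that it wants the comorbidity-inclusive association, and its Introduction keeps the two variables apart. Showing both estimates serves either aim.

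A reader might also infer three stronger things that the documents do not support:
- *That the modified frailty index is mostly a count of diseases.* The text gives no items per domain, includes function, and speaks of status, not diagnoses.
- *That the frailty estimate contains comorbidity whichever instrument is used.* For the G8 this would have to be shown.
- *That the study cannot separate the two.* The data will exist; only the planned models fail to use them.

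**Conclusion.** The gap is real and limited. The planned models cannot show how much of a frailty association is due to comorbidity, and the consequence falls on the secondary outcomes. The size is unknown: 1.08 to 1.57 is an illustration resting wholly on assumed prevalences and risk ratios, and its low end is trivial. In the middle cases a spurious significant result is more likely than 5% but is still not the usual outcome. No figure was derived for complication index or hospital stay.

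A reader might go on to infer that the primary result could be comorbidity alone. The plan's own mortality contrast is 4.3/0.6 = 7.2, which factors of this size could not produce. The point therefore casts no doubt on the choice of primary analysis. It is a cheap improvement to how the secondary results can be read.

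**What to change.** For serious complications, complication index and hospital stay:
- Keep the planned model.
- Prespecify a second model with G8 status (14 or below) as the exposure and the Charlson index added to the listed covariates.
- Report the G8 estimate with and without Charlson, in the same patients. Since the plan does not tie the degree of frailty to an instrument, both members of the pair must state that G8 is the exposure.

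Charlson alone is enough: it is the comorbidity measure that the Introduction names, and as a score it costs one parameter.

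Do not add Charlson to the modified frailty index model. Report the correlation between the two and label that estimate as frailty including comorbidity. Leave the 90-day mortality model unchanged.

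The cost is one covariate in a second set of models and one correlation, with no new data. Intervals will be slightly wider if G8 and Charlson are weakly related, and more so if they are strongly related. The adjusted estimate answers a narrower question, frailty beyond comorbidity, which is why both are shown. For serious complications, an odds ratio can shift a little when a prognostic covariate is added even without confounding, so the difference should not be read as an exact share.
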